**Figure 2. Dose Escalation Rules**

Abbreviations: DLT – dose-limiting toxicity; MTD – maximum tolerated dose

Enrollment cannot begin in a new cohort until the Safety Assessment Committee (SAC, see [Section 6.5.5](#)) has met to discuss the data from the previous dose level. Safety data will be the primary criteria for both the decision to dose escalate and for selecting the dose to be administered in the next cohort. The 25 mg BID dose has been chosen as the dose for Phase II (Section 1.3). A separate document detailing the plan for communicating decisions between the sponsor, SAC, and study sites will be provided to investigators (e.g., for dose-escalation decisions, management of DLTs, study-related modifications, etc.).

### 3.1.4. Inpatient Dose Adjustments

Dose modifications for toxicity are described in [Section 3.3.2](#).

Following Cycle 1, if no DLT-equivalent toxicity is experienced, a given patient’s dose may be maintained or escalated (provided the dose does not exceed the MTD). The decision to dose escalate a patient after Cycle 1 will be recommended by the investigator and discussed with the sponsor’s medical representative. A patient can only be escalated to a dose level at which a

minimum of 3 patients have completed Cycle 1 and which has been deemed acceptable by the SAC. Inpatient AK-01 dose escalation may occur following completion of the patient's current cycle.

Any patient who continues in the study following Cycle 1 will be assessed for toxicity and tolerability throughout their participation. The safety and tolerability of dose escalation in these patients may guide dose decisions for new cohorts.

Following completion of Cycle 1, dosing may continue in 21-day cycles until disease progression if the patient is receiving benefit and is experiencing no severe toxicity in the opinion of the investigator.

### 3.2. Overall Study Design and Plan – Phase II

Phase II will evaluate the preliminary efficacy of AK-01 in up to 4 cohorts; initially in patients with locally advanced or metastatic SCLC and BC, and subsequently, at sponsor's discretion, in patients with TNBC, SCC-HN, and OT. Up to 30 patients may be enrolled in each cohort, giving an estimated total of up to 120 patients. Since AK-01 is an experimental treatment, patients will need to have failed standard of care therapies (i.e., platinum-based therapy for SCLC; hormone therapy and a CDK4/6 inhibitor for BC; relapsed/resistant TNBC patients; standard therapy for HPV associated SCC-HN) before being enrolled in this trial.

All open cohorts in Phase II may begin enrollment concurrently and will be dosed at 25 mg BID. Dose increases will not be allowed in Phase II. Dose modifications for toxicity are described in [Section 3.3.2](#).

After Cycle 1, dosing of AK-01 may continue in 21-day cycles until disease progression if the patient is receiving benefit, and is experiencing no severe toxicity in the opinion of the investigator.

### 3.3. Toxicity Management

#### 3.3.1. Potential AEs

Based on safety data of the ongoing Phase I part of the study, the following are considered as potential AEs: bone marrow toxicity including neutropenia and thrombocytopenia; gastrointestinal toxicity including mucositis and diarrhea; and corneal deposition with blurry vision and double vision. Appropriate follow up and rapid therapy for any of these events should be undertaken

CCI

Bone marrow hypocellularity was observed in rats and dogs, with decreased hematologic correlates. Patients will be monitored for bone marrow toxicity with frequent blood counts, and should be supported with blood product transfusion and hematopoietic growth factors as

described in [Section 5.6](#). Patients should be monitored for fever and possible neutropenic fever, and treated appropriately with broad spectrum antibiotics as per institutional guidelines.

CCI

### 3.3.2. Dose Modifications for Toxicity

Dose modifications are permitted as described below for toxicities that emerge throughout the study.

IMP may be withheld for up to 21 days to allow sufficient time for recovery from toxicity, but patients who do not recover within this period will be withdrawn. Following recovery, IMP may be resumed at the same dose or at a reduced dosing frequency, depending on the type and severity of toxicity experienced (see [Table 1](#)).

[Table 1](#) describes AK-01 dose modifications for patients who experience toxicity.

**Table 1. AK-01 Dose Modifications for Toxicity**

Toxicity	Dose Modification
QTcF Prolongation	
<Grade 2	Continue at current dose level.
Grade 2 (QTcF average of triplicate readings >480 msec)	Reduce dosing frequency without interruption. If the event recurs, the dose may be withheld. If the event recurs a third time, dosing may only continue with sponsor approval.

Grade 3 (QTcF average of triplicate readings >500 msec)	Withhold AK-01 for up to 14 days. If QTcF returns to within 30 msec of baseline or <450 msec within 14 days, treatment may be resumed at a reduced dosing frequency. If the event recurs a second time, the dose may again be withheld and resumed after 14 days providing the above criteria are met after 14 days. If a third occurrence is documented, treatment must be terminated.
Grade 4 (QTcF average of triplicate readings >500 msec or >60 msec change from baseline, and TdP or polymorphic ventricular tachycardia or signs/symptoms of serious arrhythmia)	Treatment should be terminated.
Other Non-Hematologic Toxicity	
Grade ≤2	Continue at current dose level.
Grade 3 (except alopecia, nausea, vomiting or diarrhea) not optimally managed per institutional guidelines	Withhold AK-01 until event returns to Grade 1 or baseline. The first time the event occurs, maintain the AK-01 dose level when dosing is resumed.  Each time the Grade 3 event recurs, withhold AK-01 until event returns to Grade 1 or baseline, then decrease AK-01 dosing frequency- when dosing is resumed. If the event recurs at 25 mg QD, the patient will be withdrawn.
Grade 4 (except alopecia, nausea, vomiting or diarrhea) not optimally managed per institutional guidelines	Patient will be withdrawn. Patient may not be rechallenged unless discussed with sponsor and approved by the SAC.
Hematologic Toxicity	
Platelets ≤Grade 1  ANC ≤Grade 1 on Day 1 and/or ANC ≤Grade 2 on Day 8 or 15	Continue at current dose level.

Platelets  $\geq$ Grade 2,  
ANC  $\geq$ Grade 2 on Day 1,  
ANC  $\geq$ Grade 3 on Day 8 or 15,  
and/or  
 $\geq$ Grade 3 platelets or ANC with  
spontaneous bleeding at any  
time

Withhold AK-01 until platelets  $\leq$ Grade 1 and ANC  
 $\leq$ Grade 1 (Day 1) or  $\leq$ Grade 2 (Day 8 or 15). Consider  
granulocyte colony stimulating factor (G-CSF) for low  
ANC. Decrease AK-01 dosing frequency when dosing is  
resumed.

Each time the Grade 3 event recurs, withhold AK-01  
until counts recover. Consider G-CSF for low ANC. If  
the event recurs at 25 mg QD, the patient will be  
withdrawn.

**The sponsor must be notified of dose reductions. Given the P2D of 25mg BID, the only dose reduction allowed will be a reduction in dosing frequency from 25mg BID to 25mg QD.**

Following dose reduction and recovery, re-escalation of a patient's dose will be at the discretion of the sponsor in discussion with the investigator. Re-escalation must not exceed the dose at which toxicity was experienced.

### 3.4. Discussion of Design and Control

Phase I is a dose escalation study with a modified 3 + 3 design. The 3+3 design is modified to allow expansion of a cohort with 3 additional patients if 1 DLT is observed in 6 patients for a total of 9 patients in the cohort (see Figure 2). The rules-based 3 + 3 method for dose escalation is well-established, safe, and does not require real-time PK or computational modeling. Inpatient dose escalation is permitted to allow each patient to potentially receive a maximum tolerated dose of AK-01 (see [Section 3.1.4](#)). In Phase II, preliminary efficacy of AK-01 will be assessed in up to 4 cohorts (BC, SCLC, TNBC, SCC-HN and/or OT). Preclinical evidence indicates AK-01 may be particularly efficacious in these tumor types.

Since this is not a comparison study, the use of a placebo control is not applicable.

### 3.5. Estimated Duration of the Study

The estimated duration for the entire study is 4-5 years from the time the first patient is enrolled in the study until the last patient visit.

### 3.6. Determination of Sample Size

In Phase I, the 3 + 3 design dose escalates cohorts of up to 9 patients until the MTD is identified. Up to 6 additional patients may be dosed to inform the selection of a P2D. A sample size of approximately 30 patients was considered sufficient to identify the MTD and is not powered on the basis of statistical hypothesis testing.

In Phase II, up to 30 patients for each tumor type will be administered IMP (up to 120 patients total). An observed ORR (proportion of partial or complete responders by RECIST) of  $\geq 20\%$  with

a durability of at least 4 months will be considered evidence of efficacy. With 15 patients in a cohort, there is approximately 60% power to reject the null hypothesis of the ORR being  $\leq 5\%$  when the true ORR is 20% using a one-sided exact test for a single proportion at a significance level of 0.05. The power for this statistical test for a single tumor type without any adjustment for multiplicity is provided in [Table 2](#) using various observed ORRs.

**Table 2. Statistical Power of Observed Overall Response Rates**

True ORR	10%	15%	20%	25%	30%
N=15	18%	40%	60%	76%	87%
N=20	13%	35%	59%	78%	89%

Thus, whenever the true ORR is at least 20%, a sample size of 15 or 20 patients per tumor type provides approximately 60% power to reject the null hypothesis.

### 3.7. Study Completion

The study will be considered complete when all patients enrolled in Phase II have completed at least 8 cycles of treatment, experienced disease progression, or discontinued IMP (or unacceptable toxicity in the first cohort of Phase I prevents further dose escalation).

Once a given patient in Phase I or II has completed 8 cycles of treatment, AK-01 administration may continue until disease progression, so long as the patient is receiving benefit and is experiencing no severe toxicity in the opinion of the investigator. During this period, study assessments will be performed as described in Appendix 1. For patient discontinuation procedures, see [Section 4.2.1](#).

### 3.8. End of Trial

The end of trial occurs following study completion, after the last patient has discontinued IMP and completed any applicable follow-up ([Section 3.7](#)). “End of trial” refers to the date of the last visit or last scheduled procedure for the last patient in the study.

## 4. STUDY POPULATION

### 4.1. Criteria for Enrollment

#### 4.1.1. Inclusion Criteria

Patients who meet all of the following inclusion criteria will be eligible for enrollment in the study:

1. Are  $\geq 18$  years of age.
2. Have given written informed consent prior to any study-specific procedures.
3. Are willing to make themselves available for the duration of the study, and are willing to follow study procedures.
4. Have a performance status of 0 or 1 on the Eastern Cooperative Oncology Group (ECOG) scale (see Appendix 4).
5. Have an estimated life expectancy of  $\geq 12$  weeks.
6. Have adequate organ function including:
  - a. Hematologic: ANC  $\geq 1.5 \times 10^9/L$ , platelets  $\geq 100 \times 10^9/L$ , and hemoglobin  $\geq 90$  g/L. Patients may receive red blood cell transfusions to achieve this hemoglobin level at the discretion of the investigator.
  - b. Hepatic: Albumin  $\geq 30$  g/L, bilirubin  $\leq 1.5$  times ULN, ALT and AST  $\leq 2.5$  times ULN. If the liver has tumor involvement, AST and ALT  $\leq 5$  times ULN are acceptable.
  - c. Renal: Estimated glomerular filtration rate (eGFR)  $\geq 45$  mL/min/1.73 m^2 (see Appendix 3)
7. Have discontinued all chemotherapy, investigational therapy, molecularly targeted therapy, and cancer-related hormonal therapy at least 14 days prior to study enrollment (6 weeks for mitomycin-C or nitrosoureas).
8. Have discontinued biologic therapy and immunotherapy at least 21 days prior to study enrollment or have recovered from all AE to baseline or Grade 1 with the exception of alopecia or Grade 2 neuropathy.
9. Patients who have had radiation therapy must be fully recovered in the opinion of the investigator prior to enrolling on study.
10. Are recovered or recovering from the acute adverse effects of any chemotherapy, biologic therapy, immunotherapy, molecularly-targeted therapy, cancer-related hormonal therapy, and investigational therapy ( $\leq$ Grade 1 or baseline), with the exception of alopecia or Grade 2 neuropathy.
11. Have received at least 1 but no more than 4 lines or regimen of prior systemic therapies for locally advanced or metastatic disease. Hormone therapies are not considered in the determination of number of prior lines of systemic therapies.
12. Patients who have had surgery must be fully recovered in the opinion of the investigator prior to enrolling on study.

13. Female patients with reproductive potential must agree to use 2 forms of highly effective contraception during the study and for at least 3 months following the last dose of IMP. Sexually active male patients must use a barrier method of contraception (condom) during the study and for at least 3 months following the last dose of IMP.
14. Females with child-bearing potential must have had a negative pregnancy test result  $\leq 28$  days prior to the first dose of IMP, as well as  $\leq 1$  day prior to the first dose of IMP.
15. Patients must be, in the judgment of the investigator, appropriate candidates for experimental therapy, and no standard therapy would confer clinical benefit to the patients.

#### Phase I

16. Patients must have histological or cytological evidence of cancer (solid tumors, excluding primary brain tumor) that is evaluable, and locally advanced and/or metastatic.

#### Phase II

17. Patients must have disease that is measurable by RECIST v.1.1 (see Appendix 10).
18. Patients must have histological or cytological evidence of a solid tumor that is locally advanced and/or metastatic and have failed locally approved therapies that have clinical benefit as follows:
  - a. SCLC
    - Must have failed platinum-containing therapy but be in a platinum sensitive relapse (having responded to up to 6 cycles of platinum therapy with at least SD, PR, or CR, and then maintained that response without progression for 3 months after the last platinum dose. Patients could have received maintenance therapy following the completion of platinum therapy. Patients who never responded or progresses  $< 3$  months after the last platinum dose are not eligible).
  - b. BC
    - ER+ and/or PR+ but HER2-negative (see Appendix 8 for eligible biomarker expression).
    - May have failed up to 2 prior chemotherapy regimens.
    - Must have failed a hormone therapy and a CDK4/6 inhibitor.
  - c. TNBC
    - Must have recurrent/refractory TNBC, defined as any breast cancer that expresses  $< 1\%$  ER,  $< 1\%$  PR, and is HER2-negative (immunohistochemistry staining of 0 or +1, or no evidence of amplification using single or dual- probe- in situ hybridization). Must have failed standard therapy.
  - d. SCC-HN
    - For HPV associated SCC-HN, must have failed standard therapy.
  - e. OT

- To be determined by the sponsor.

#### 4.1.2. Exclusion Criteria

Patients who meet the following criteria will be excluded from the study:

19. Have medical conditions that, in the opinion of the investigator, would preclude participation in this study such as overwhelming infections.
20. Have symptomatic central nervous system (CNS) metastasis. Patients with treated CNS metastasis are eligible if they are asymptomatic and not currently receiving corticosteroids. Screening of asymptomatic patients without a history of CNS metastasis is not required.
21. Have a primary tumor of the CNS.
22. Have a history of organ transplant (e.g., heart, lungs, liver, bone marrow, or kidney).
23. Females who are pregnant or nursing.
24. Have symptomatic human immunodeficiency virus (HIV) infection, known HIV positive test results or have chronic active hepatitis B or C (screening is not required).
25. Have clinically significant cardiac disease including any of the following:
  - A history of congenital long QT syndrome, symptomatic bradycardia, ventricular arrhythmia, uncontrolled atrial fibrillation, second or third degree heart block, or other conduction abnormality that in the opinion of the investigator would preclude safe participation in this study.
  - Congestive heart failure (New York Heart Association Class  $\geq 3$ ; see Appendix 5).
  - Unstable angina pectoris, acute myocardial infarction, or stroke  $\leq 12$  months prior to enrollment.
  - QTcF prolongation  $>450$  msec.
26. CCI [REDACTED]
27. Have  $>$ Grade 1 hypokalemia, hypomagnesemia, or hypocalcemia which cannot be controlled prior to enrollment.
28. Have a history of major surgery to the upper gastrointestinal (GI) tract, GI disease or other medical condition that in the opinion of the investigator may interfere with oral drug absorption.
29. Are a family member of the investigator or staff of the study site.
30. Are currently enrolled in another clinical study of an investigational therapy.
31. Previous therapy with an Aurora kinase inhibitor.
32. Hypersensitivity to any components of AK-01.

## 4.2. Discontinuation

### 4.2.1. Discontinuation of Patients

In accordance with the guidelines of the International Conference on Harmonisation (ICH) Good Clinical Practices (GCP), Health Canada, European Medicines Agency, and United States Food and Drug Administration, a patient may withdraw their participation in this study at any time.

Criteria to discontinue patients from study treatment will include but will not be limited to:

- Objective disease progression based on RECIST v. 1.1 as determined by the investigator
- Unacceptable toxicity
- Significant protocol violation
- Global deterioration of health status
- Lost to follow-up
- Refusal of further treatment by patient
- Study termination by sponsor
- Dosing is delayed by more than 21 days due to toxicity

Reasons for discontinuation from the study may include:

- Study termination by sponsor
- Lost to follow-up
- Withdrawal of consent

If a patient is found to not meet the enrollment criteria but was inadvertently enrolled, the patient must be discontinued from the study and the sponsor or its designee must be informed. An exception to this requirement may be granted in rare circumstances where the patient has a serious or life threatening condition for which there is no effective alternative therapy and, in the opinion of the investigator, is receiving benefit from study treatment. In this case, the investigator must obtain documented approval from the sponsor's medical representative to allow the patient to continue receiving IMP.

Following discontinuation or withdrawal, the investigator will request that the patient return all unused IMP and packaging, and participate in the Discontinuation and 30-Day Follow-up visits. If it is in the best interest of the patient to start a new anti-cancer treatment prior to this date, the follow-up assessments may be performed sooner, so long as they are completed prior to initiation of the new therapy.

The primary reason for withdrawal, patient outcome, and the date of withdrawal will be documented. Every effort will be made to adequately follow the patient for any unresolved AEs. In the case of withdrawal due to global deterioration of health status, the signs, symptoms, or results that motivated this decision will be documented.

If the patient withdraws from the study and also withdraws consent for disclosure of future information, no further evaluations will be performed and no additional data will be collected. The sponsor may retain and continue to use any data collected before the withdrawal of consent.

Discontinued patients may be replaced in the study, as described in [Section 5.3.2](#).

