not be reported as SAEs, however if an AE occurs during hospitalization for preplanned surgery that meets the above criteria, it will be reported as an SAE. SAEs due to progressive disease (including death) should not be reported as SAEs unless the investigator also deems there is a possible contribution of the IMP.

All SAEs occurring from the time the patient signs the ICD until the 30-day Follow-up visit must be reported to the sponsor or its designee regardless of relatedness to IMP or protocol procedures. Thereafter, SAEs will be reported only if the investigator feels the events were related to the IMP or a protocol procedure. Any SAEs after ICD signature and prior to administration of IMP will be reported if the investigator feels the events were related to a protocol procedure.

Appendix 1 outlines specific safety assessments for the 30-day Follow-up visit. All drug-related AE and SAEs will be followed until the events resolve, the events are no longer considered to be drug-related, the patient dies or is lost to follow-up, or until a new treatment is initiated for the patient. Frequency of follow-up evaluation is left to the discretion of the investigator.

The medical representative of the sponsor will monitor safety data throughout the course of the study. The sponsor and/or its designee will review SAEs within appropriate timeframes to meet reporting obligations imposed by regulatory authorities. All serious and unexpected AEs for this study will be reported to regulatory authorities in accordance with local laws, directives and regulations.

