- v. Patients will attend a follow-up visit 30 days (+/- 7 days) following the last dose of IMP.
- w. Patient survival will be confirmed approximately every 3 months for up to 1 year.

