### 9.8.2. Adverse Events

Detailed definitions and classification of AEs are specified in the Protocol, Section 6.5.3. All AEs will be coded using the MedDRA version 20.0 terminology and graded using NCI CTCAE v. 4.03.

A treatment-emergent AE is an AE that started or worsened (i.e. increased in severity) from the Treatment start date to 30 days after the Treatment end date. Only treatment-emergent AEs will be summarized in the tables. All AEs entered in the eCRF will be listed and AEs not considered as treatment-emergent will be flagged.

The data will be presented by cohort, see Section 7.6 regarding an assignment of particular AEs to the cohorts.

The number and frequency of patients reporting each treatment-emergent AE will be summarized by primary System Organ Class (SOC) and Preferred Term (PT), where subjects with more than one AE within a particular SOC and PT are counted only once for that SOC and PT.

To assess the relationship of the AE to administration of AK-01, the following terminologies are defined by the protocol: probably related, possibly related, unlikely, not related. For tables summarizing AEs related to AK-01, the options probably related and possibly related will be considered.

The following AE summaries will be presented (sorted alphabetically unless specified otherwise):

- Treatment-emergent adverse events, by SOC and PT
- Treatment-emergent adverse events in Cycle 1, by SOC and PT
- Treatment-emergent adverse events related to AK-01, by SOC and PT
- Treatment-emergent adverse events, by PT (sorted by overall decreasing frequency)
- Treatment-emergent adverse events in Cycle 1, by PT (sorted by overall decreasing frequency)
- Treatment-emergent adverse events related to AK-01, by PT (sorted by decreasing frequency)
- Treatment-emergent adverse events, by PT and maximum CTCAE grade (sorted by overall decreasing frequency)
- Treatment-emergent adverse events related to AK-01, by PT and maximum CTCAE grade (sorted by overall decreasing frequency)

- Treatment-emergent adverse events leading to dose reductions or interruptions, by SOC and PT
- Treatment-emergent adverse events related to AK-01 leading to dose reductions or interruptions, by SOC and PT
- Discontinuations due to adverse event, by SOC and PT
  - These events will be identified as AEs that have “Action taken with study drug” reported as “Drug withdrawn” AND at the same time, in the “Discontinuation page”, the reported reason is “Unacceptable toxicity”.

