- Discontinuations due to adverse event related to AK-01, by SOC and PT
- Treatment-emergent serious adverse events, by SOC and PT
- Treatment-emergent serious adverse events related to AK-01, by SOC and PT
- Dose-limiting toxicities, by SOC and PT (phase I only)
- DLT-equivalent toxicities, by SOC and PT

Deaths will be summarized by reason (AE/disease progression/other), and those caused by an AE by SOC and PT. Three types of tables will be prepared:

- On-treatment deaths (i.e. all deaths occurring up to 30 days after the Treatment end date)
- On-treatment deaths related to AK-01
- All deaths

An overall summary of AEs will be presented and will include frequency and percentage of patients with:

- Any treatment-emergent adverse event
- Any treatment-emergent adverse event in Cycle 1
- Any dose-limiting toxicities
- Any treatment-emergent adverse event related to AK-01
- Any treatment-emergent adverse event leading to dose reductions or interruptions
- Discontinuations Due to Adverse Event
- Any treatment-emergent serious adverse event
- On treatment deaths due to adverse event
- On treatment deaths due to adverse event related to AK-01

The following AE listings will be presented:

- Adverse events
- Dose-limiting toxicities

- Serious adverse events
- Adverse events leading to dose reductions or interruptions
- Adverse events leading to discontinuation (listing the same events as in the table “Discontinuations due to adverse event”).
- Deaths

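### All-cause SAE reporting ends at a follow-up visit that may fall before Day 30, while the SAP counts treatment-emergent SAEs to a fixed Day 30; for non-serious AEs the same mismatch is wider

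*Protocol*

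**What the plan says.** **Collection of SAEs.** Protocol 6.5.4: "All SAEs occurring from the time the patient signs the ICD until the 30-day Follow-up visit must be reported", whatever their cause. It then narrows the duty: "Thereafter, SAEs will be reported only if the investigator feels the events were related to the IMP or a protocol procedure". The change of rule is tied to a visit and not to a date.

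**When the visit happens.** Appendix 1, note v (the current schedule is headed Phase II): "Patients will attend a follow-up visit 30 days (+/- 7 days) following the last dose of IMP". That permits Day 23 to Day 37. Protocol 4.2.1 asks patients who stop to attend the Discontinuation and 30-Day Follow-up visits, and then makes an exception for those whose interest lies in moving to other cancer therapy before the visit is due. For them, "the follow-up assessments may be performed sooner, so long as they are completed prior to initiation of the new therapy". It gives no earliest day, and it does not say that all-cause reporting continues to Day 30 after an early visit.

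**Analysis.** SAP 9.8.2 calls an AE treatment-emergent if it starts or worsens "from the Treatment start date to 30 days after the Treatment end date". The definition does not stop at the follow-up visit or at the start of another therapy. The planned tables include "Treatment-emergent serious adverse events, by SOC and PT", and a separate table is restricted to related SAEs.

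**Non-serious AEs.** Protocol 6.5.3 collects AEs of any cause only up to the last dose. Later AEs are reported only if they are ongoing or judged related.

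**The concern.** The all-cause SAE table would be filled under two collection rules. Up to the follow-up visit it receives every reportable SAE. From the visit to Day 30 it is guaranteed only those judged related. A reader of the table cannot tell which rule applied to which patient or day.

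Two consequences follow. The all-cause count is too low wherever the visit falls before Day 30. The related share of tabulated SAEs is pushed upwards, because related events stay reportable and unrelated ones do not.

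Part of the shortfall also depends on clinical course. The open-ended early visit applies only to patients who move to another anti-cancer treatment, and for them the remaining days to Day 30 include time on a different drug. Safety and tolerability is a secondary objective in both phases, so the tables should state accurately what period of collection they represent.

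**Working it through.** The plan states no figure for this point, so there is nothing to reproduce. The check compares the two windows.

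**Inputs**
- End of all-cause SAE reporting: the follow-up visit, on day d after the last dose (Protocol 6.5.4).
- Permitted d: 23 to 37 (Appendix 1, note v); earlier for switchers, with no stated minimum (Protocol 4.2.1).
- End of the treatment-emergent window: Day 30 after the last dose (SAP 9.8.2).
- End of all-cause non-serious AE reporting: the last dose, Day 0 (Protocol 6.5.3).

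**Step 1: gap per patient.** Uncovered days = max(0, 30 − d); share of the 30-day tail = max(0, 30 − d)/30.

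| Visit day d | Basis | Uncovered days | Share of tail |
|---|---|---|---|
| 30 or later | within visit window | 0 | 0% |
| 23 | earliest under visit window | 7 | 23% |
| 21 | switcher, illustrative | 9 | 30% |
| 14 | switcher, illustrative | 16 | 53% |
| 7 | switcher, illustrative | 23 | 77% |

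Only the Day 23 row is fixed by the documents. The last three rows are assumptions.

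**Step 2: share of a cohort's tail.** Suppose a fraction s switches with a visit on day d and everyone else is seen at Day 30 or later. The uncovered share is s × (30 − d)/30. For s from 10% to 50% and d from 7 to 21 (assumed ranges):
- lowest: 0.10 × 9/30 = 3%;
- highest: 0.50 × 23/30 = 38%;
- s = 50%, d = 14: 0.50 × 16/30 = 27%.

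**Step 3: share of the whole window.** The table covers treatment plus tail. For a patient who stops after two 21-day cycles (assumption), it spans 42 + 30 = 72 days. A Day 23 visit leaves 7/72 = 10% uncovered. The case s = 50%, d = 14 leaves 0.50 × 16/72 = 11%. Longer treatment lowers both.

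**Step 4: what a common end date recovers in switchers.** If collection and analysis both stop when new therapy starts on day t, the days recovered are t − d. With d = 14, s = 50% and t − d between 1 and 7 days (assumption), that is 0.50 × 1/30 = 2% to 0.50 × 7/30 = 12% of the tail. The other 30 − t days leave the window.

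**Step 5: other sources.** In Appendix 1, AE monitoring stops at the 30-Day Follow-up column, and the three-monthly column holds survival only. No later scheduled contact would recover a non-fatal unrelated SAE. SAP 2 lists only the change of biopsy type as a departure from the protocol, so the mismatch is not acknowledged.

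**Step 6: non-serious AEs.** With all-cause reporting ending at Day 0, the gap is 30 − 0 = 30 of 30 days for every patient.

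**The case against.** The strongest reply is that little is lost. Related SAEs remain reportable after the visit. SAEs due to progression are not reported as SAEs at all unless AK-01 may have contributed (Protocol 6.5.4). Unknown causality is treated as related (Protocol 8.2, SAP 9.1.3). Deaths should be found through survival follow-up (Protocol 6.7.2) and are tabulated to Day 30 (SAP 9.8.2). The safety analysis is descriptive, and no decision rule uses the related share of SAEs. All of this stands, and it narrows the affected events to mainly non-fatal, unrelated, non-progression SAEs.

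It is also fair to say that 4.2.1 never states that an early assessment moves the cut-off in 6.5.4. That link is the natural reading, because the exception directly follows the sentence naming the 30-Day Follow-up visit, but it is a reading. The Day 23 gap does not need it.

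A reader might infer that a half or more of post-treatment SAE information is lost in switchers. The documents do not support that. They give no switching frequencies or times, the large percentages use the tail alone as denominator, and many of those days would be spent on another drug. Nor is the loss confined to switchers, since the ±7-day allowance is not limited to them. Finally, uncovered means not required to be reported; sites may still report such events.

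**Conclusion.** The mismatch is real and modest. SAP 9.8.2 presents as all-cause a period in which, after an early visit, only related SAEs must be reported. The size that rests on the documents alone is up to 7 of the 30 tail days (23%). For switchers the gap has no stated limit, and any larger figure is an assumption. Converting uncovered days into a share of unrelated SAEs also assumes a constant event rate over the tail.

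The under-count goes in one direction and, in switchers, is linked to clinical course. Neither the Phase I DLT assessment nor the Phase II ORR analysis is touched, and the documents do not support saying that deaths or related SAEs are lost. The wider problem of the same kind is non-serious AEs, where the full 30-day tail lacks all-cause collection in every patient.

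**What to change.** 1. In Protocol 6.5.4, end all-cause SAE reporting on a date and not at a visit: 30 days after the last dose, or the start of new anti-cancer therapy if earlier, whenever the visit is held.
2. In SAP 9.8.2, end the treatment-emergent SAE window on that same date for each patient.
3. Reconcile Protocol 6.5.3 with the SAP window for non-serious AEs. Either extend all-cause AE reporting to the same date, or limit the all-cause non-serious AE tables to the period in which such AEs are collected.

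For patients seen early who do not switch, this closes the gap. For switchers it mainly removes days that the table mislabels as all-cause follow-up, and it recovers only the days between the visit and the new therapy. Follow-up length will then differ between patients and should be reported.

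The SAE change costs one sentence in each document, plus a phone or record check at Day 30 for patients seen early who have not switched. The start date of new therapy must be on record. The BOR definition in SAP 6.1 already depends on the start of additional treatment, but Protocol 5.6 records concomitant medication only to the last dose, so the sponsor should confirm that the date is captured. Extending non-serious AE collection would add site work; limiting the tables would not.
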